Phase II Study Drug and Dosing	
 • Participants will receive 5-FC 60mg/kg/day for 10 days. • Participants will receive IV AMB 0.7-1.0 mg/kg/day for 7 days. • Liposomal Amphotericin B single IV dose 10 mg/kg is preferred, when available. • All participants will receive fluconazole 1200 mg/day during consolidation therapy from day 1 to 14 then 800 mg/day from day 15 to 10 weeks, and 200mg/day after 10 weeks.
Phase II Monitoring	
 • All participants will have CSF quantitative fungal cultures performed on Days 1, 2-4, 5-7, and 10-14 of antifungal treatment. • 3x weekly CBC, chemistries, and kidney function tests for duration of induction therapy during hospitalization
Phase II Safety Analysis	
The Data Monitoring Committee (DMC) will conduct interim safety analysis after 10 participants are enrolled with >2 weeks of accrued data and calculable EFA.
 
EFA and culture positive Cryptococcus relapse will be monitored by the trial investigators, and if statistical evidence shows that EFA <0.2 log₁₀ CFU/mL/day, then an early DMC will be called.

Phase II Statistical Design Rationale	
Early fungicidal activity (EFA) is a quantitative measure of antimicrobial activity for an antifungal regimen in human patients with cryptococcal meningitis. In numerous trials, EFA correlates well with 10-week mortality. Specifically, EFAs worse than 0.20 log₁₀ CFU/mL/day are associated with higher mortality (>50%) and EFA better than 0.3 log₁₀ CFU/mL/day is associated with lower mortality (30-40%).
 
EFA is calculated by measuring the slope of the clearance rate of yeast from CSF, which is calculated from longitudinal quantitative CSF cultures collected over two weeks.
 
By intent to treat analysis, all participants who are enrolled in this study will be included for analysis.

Clinical Trial Sites	
 1. Mulago Hospital, Kampala, Uganda 2. Kiruddu Hospital, Kampala, Uganda 3. Mbarara Regional Referral Hospital, Mbarara, Uganda

Estimated Time to Complete Enrollment:	Up to 12 months
---	-----------------

Table of Contents

1. KEY ROLES	1
2. BACKGROUND AND SCIENTIFIC RATIONALE	2
2.1 Background Summary and Study Hypotheses	2
2.2 Burden of Cryptococcal Meningitis	2
2.3 Treatment of Cryptococcal Meningitis	4
2.4 Rationale for Optimizing 5FC Dose	6
2.5 Early Fungicidal Activity	7
2.6 Potential Risks and Benefits	10
3. OBJECTIVES	12
3.1 Study Objectives	12

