2.2 Burden of Cryptococcal Meningitis

Cryptococcal meningitis has become the most common cause of adult meningitis in many parts of Africa,¹³ where cryptococcosis now rivals tuberculosis in all-cause mortality.¹⁴ While long-term survival has improved with widespread use of antiretroviral therapy in high-income countries, early mortality remains high.¹⁵ Furthermore, expanding access to antiretroviral therapy in resource-limited

settings has not yet led to compelling improvements in mortality, with 10-week mortality rates between 24% and 37%, even under optimal research conditions.^{16,17} Early mortality rates are often ~70% in routine practice where access to diagnostics or medications is limited or unavailable, intracranial pressure is uncontrolled, or in settings where other barriers to the management of cryptococcal meningitis exist.^{18–20} Intravenous administration of amphotericin B deoxycholate is not often possible in resource-limited settings, even when it is available.

Even with amphotericin-based induction therapy, survival is not optimal. Figure 2.2 displays the survival in Uganda from 2013-2017 in the setting of a study using IV amphotericin + fluconazole induction therapy and control of intracranial pressure.^{21,22} Approximately, half of the mortality occurs during the first two weeks and the other half during the next 18 weeks, particularly in the first 6 weeks (Figure 2.2). This 18-week time period captures 95% of the 5-year mortality in Uganda.²³

Figure 2.2: Survival After Cryptococcal Meningitis by Glasgow Coma Scale (GCS) in Uganda

GCS < 15 = altered mental status, GCS = 15 = intact mental status, responsive to voice

The efficacy and safety of induction therapy for cryptococcal meningitis can be evaluated effectively with all-cause mortality as an early clinical outcome. This is because approximately half of the mortality related to CM occurs during the first two weeks.²⁴ 18-week outcomes will also be assessed for further evaluation of primary and secondary endpoints.

Table 2.2: The 2-week mortality of Ugandans on Amphotericin + Flucytosine with GCS=15

Study	Number of Patients	Number Died	2-week Mortality	95% Confidence Interval
EnACT Stage 1-3	25	1	4.00%	-3.7%, 11.7%

Jarvis et al. NEJM 2022; Uganda GCS=15 data	197	17	8.60%	4.7%, 12.6%
Average	222	18	8.10%	4.5%, 11.7%

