Shortcomings in EFA: EFA is not a perfect surrogate marker for all-cause mortality on an individual patient level basis. Thus, EFA has been criticized.⁴⁸ There are two problems with EFA: 1) Persons who rapidly die after diagnosis may not have a computed EFA (as an EFA requires at least two time points); 2) Death in persons with advanced AIDS could be from other opportunistic infections and/or AIDS-related cancers; 3) Death after cryptococcal meningitis is influenced also by the immune system. As we have reported, cryptococcal meningitis follows the “damage-response framework for microbial pathogenesis”⁴⁹—whereby those with the worst immune response (e.g. lowest CD4 T cell count) and highest pathogen burden have high mortality—but surprisingly those with highest CD4 counts and lowest fungal burden (i.e. sterile CSF cultures), actually have relatively higher mortality as well (Figure 2.5.C).⁵⁰ Similarly, over abundant immune responses, e.g. unmasking cryptococcal IRIS occurring early after HIV therapy initiation, is highly detrimental.⁵¹ Excess dysregulated inflammation in the brain is often fatal.

Thus, EFA cannot capture all factors associated with mortality, but EFA can assess the microbiologic activity of an antifungal regimen. At present, there is no immune directed therapy for cryptococcosis, thus the only therapeutics we have (and that are FDA-approved) are focused on antifungal therapy. Thus, while the immune system contributes to mortality on an individual patient basis, the group EFA of an antifungal regimen has been associated with overall mortality as displayed in Figures 2.4.B.

In this trial, the primary endpoint is EFA as the clearance rate of *Cryptococcus* yeast in CSF. EFA is a direct quantitative measure of the antimicrobial activity of 5-FC used in combination with AMB therapy in humans with cryptococcal meningitis.

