2.6 Potential Risks and Benefits

2.6.1 Potential Risks

First, the EFA, which as described above, indicates the rate of fungal clearance and correlates with mortality due to CM will be followed by the study team. If EFA is consistently $<0.2 \log_{10}$ CFU/mL/day after 10 enrolled patients, then the trial will be suspended until an interim review

can be completed. In addition, all patients will be receiving IV AMB which is also a gold standard therapy and reduces mortality related to CM, in addition to fluconazole.

As discussed above 5-FC is a critical aspect of the induction phase of treatment for CM, decreasing the fungal burden in the CNS and improving mortality. Given this, there is a risk that decreasing the dose of 5-FC will lead to insufficient CSF concentrations to achieve fungal clearance and reduced mortality. For this reason, we will implement several safety measures.

As discussed above, our trial will use the induction therapy regimen established in the AMBITION-cm trial and now recommended by the updated WHO guidelines.⁴ During phase 2 of that trial, high dose liposomal Amphotericin B with fluconazole achieved an EFA of $-0.52 \log_{10}$ CFU/mL/day.³⁸ These data provide strong evidence that optimizing the dose of 5-FC can be safely studied in the same context without significantly reducing mortality.

The risks associated with the traditional IV AMB include nephrotoxicity, life-threatening hypokalemia (common), life-threatening hypomagnesemia (common), severe anemia (common), nausea (common), vomiting (common), diarrhea (common), severe infusion reactions including rigors, local inflammation, and thrombophlebitis (common), and many other less common side effects.

Amphotericin B is an FDA pregnancy category B (no evidence of risk in humans); however, all participants will also receive flucytosine and fluconazole, which are both potential teratogens at high doses. Therefore, subjects must use effective forms of contraception to avoid becoming pregnant. Pregnant women will be excluded.

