The control cohort will be drawn from the AMBITION trial that was conducted partly in Uganda.⁴³ This was a randomized clinical trial that evaluated single high-dose amphotericin B (10 mg/kg) with fluconazole (1200 mg/day) and flucytosine (100 mg/kg/day) for 2-week induction therapy of cryptococcal meningitis compared to standard amphotericin deoxycholate (1 mg/kg/day) with flucytosine (100 mg/kg/day). The trial enrolled participants who were HIV positive with a first episode of cryptococcal meningitis diagnosed by cryptococcal antigen or India ink staining. Participants were excluded if they were pregnant, had already taken amphotericin or fluconazole for >48 hours, had a previous serious reaction to the study medications or were taking a medication that would be contraindicated with the study medications. In Uganda, the trial enrolled 163 participants in the control arm and 164 in the intervention arm for a total enrollment of 327 Ugandan participants. The control cohort will be drawn from Ugandan participants. If IV liposomal amphotericin B is used in the investigational cohort then they will be drawn from the intervention arm. If IV deoxycholate amphotericin B is used in the investigational cohort then they will be drawn from the control arm. We will compare the EFA of all the control participants to the interventional participants using multivariate mixed linear regression, adjusting for confounding factors such as CD4+ count, GCS<15 or not, prior exposure to ART or not and other important clinical factors. We will also compare 10-week survival in the

interventional and control cohorts, using multivariate Cox regression, adjusting for the same clinical factors as the mixed regression model.

This 2018 and 2022 WHO recommended regimen is based on a phase III randomized clinical trial demonstrating that:

- i) 1 week of IV AMB had equivalent survival as 2 weeks of IV AMB;²
- ii) 1 week of IV AMB combination therapy was less toxic than 2 weeks of IV AMB;² and
- iii) Adjunctive flucytosine had superior survival to adjunctive fluconazole.²

A DSMB review by the full committee will occur after 10 participants have been enrolled with >2 weeks of accrued data. A local Ugandan community member will be invited to attend open DSMB meetings. The DSMB safety reports will be submitted to the IRBs and regulatory authorities.

Timing of ART Initiation or Switch.

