5. STUDY ENROLLMENT AND WITHDRAWAL

5.1 Inclusion Criteria

- CSF cryptococcal antigen (CrAg) positive meningitis
- Ability and willingness to provide informed consent
- Willing to receive protocol-specified lumbar punctures

Exclusion Criteria

- Age < 18 years
- Inability to take enteral (oral or nasogastric) medicine
- Cannot or unlikely to attend regular clinic visits
- Receiving chemotherapy or corticosteroids
- Suspected paradoxical immune reconstitution inflammatory syndrome (IRIS)
- Pregnancy or breastfeeding (tested on screening)
- CrCl < 20 mL/minute*
- Absolute neutrophil count < 500 x 10⁶ cells/L*
- Thrombocytopenia < 50,000 x 10⁶ cells/L*
- Patients with prior 5-flucytosine exposure ≥3 days in the 12 months prior to enrollment
- Any condition for which participation would not be in the best interest of the participant or that could limit protocol specified assessments.

Rationale for Phase II Trial Criteria

The inclusion and exclusion criteria of the Phase II trial are meant to be broad to enroll a representative sample of persons in resource-limited areas, and thereby be broadly generalizable. Flucytosine and fluconazole are known teratogens in the first trimester. Amphotericin is the preferred drug of choice during pregnancy. Since therapy includes flucytosine or fluconazole, pregnant and breastfeeding women are excluded.

Other exclusion criteria are intended to minimize bias and maximize likelihood of completing the study or need to customize therapy (e.g., pregnant women).

Note on subjects with positive CSF CrAg but subsequent negative CSF cultures:

Since CSF CrAg is more sensitive than CSF culture in very early disease with a low fungal burden,^{18,54} CSF culture-negative patients with a positive CSF CrAg will be assumed to have early CM and be eligible for the study and included in the analyses. Approximately 10-15% of participants are estimated to be culture negative. CSF cultures take 7-14 days for results, thus are not a realistic criterion for enrollment as therapy is initiated based on CSF CrAg results. CSF

CrAg LFA is markedly more sensitive than India ink microscopy.⁵⁴ Although these participants will not contribute to the quantitative CSF clearance data, they will contribute to all other endpoints for survival, safety, tolerability, and toxicity – all of which are important outcomes.

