10.3 Data and Safety Monitoring Board (DSMB) Safety Reviews

Refer to the DSMB Charter for full details.

- DSMB safety reviews will occur after 10 participants have been enrolled and have accrued approximately 2 weeks of follow-up data.

The DSMB committee will consist of [name] as the chairperson, [name], [name], [name], and [name]. The trial PIs and statistician will present to the DSMB in an open session before the DSMB enters into a closed, private session. A quorum of three members will be required to meet, including the DSMB statistician. A local Ugandan community member will be invited to attend open DSMB meetings. The PhD study biostatistician will prepare summary progress reports on tolerability, safety, and efficacy within approximately 30 days of 10 participants being enrolled and accruing 2 weeks of follow up data. At time of the safety reviews, all available data will be utilized, particularly with respect to control subjects.

Data are unblinded, thus the PI, on-site investigators, and other team members will additionally monitor for any unexpected concern. If concerns are raised, this will prompt an unscheduled DSMB safety evaluation.

If there are unexpected safety concerns of serious and potentially related AEs, these AEs will be reviewed by the DSMB, and reported to the relevant regulatory authorities with oversight. Unexpected safety concerns may result in suspension of further trial interventions or closure to further enrollment. The study PIs, DSMB chair, and sponsor each retain the authority to suspend additional enrollment and study interventions for the entire study; however, consensus agreement will be sought. Examples of findings that might trigger a safety review are the number of SAEs overall, the number of occurrences of a particular type of SAE, severe AEs/reactions, or increased frequency of events. In particular, the investigators will be monitoring for culture positive Cryptococcal relapse. This has been rare in previous trials and a small number of cases would be cause for an early safety review. The biostatistician will perform a formal analysis as per the statistical plan.

Reporting to the IRB of record will occur with annual reporting, and after each DSMB report. We will report all deaths, including cryptococcal related deaths to the IRB.

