11.4.1 Sample Size & Statistical Power

Similar to phase II TB trials, rate of CSF yeast clearance has been used in moderate size phase II cryptococcal trials to demonstrate microbiologic efficacy as proof of concept. When the EFA is better than 0.20 CFU/mL/day, there is reasonably good survival after cryptococcal meningitis (Figure 2.5). Once the EFA is better than approximately 0.30 \log_{10} CFU/mL/day, there is less obvious incremental gains in survival beyond this threshold.⁶¹

Overall, the EFA is a quantitative measure of microbiologic activity in humans of an antifungal regimen.

For the EFA on a lower-dose 5-FC, we will have 36 participants with adequate data to calculate the EFA (i.e. non-sterile CSF culture at baseline and at least 1 follow up LP) and a standard deviation of approximately 0.20.

The CSF EFA will be interpreted in the context of other antifungal regimens published EFAs and the concurrent controls (Table 2.5). For example, if the lower-dose 5-FC arm has an EFA >0.30 \log_{10} CFU/mL/day and standard deviation of ± 0.20 , then the low dose 5-FC regimen will establish superiority compared to fluconazole 1200 mg regimen and non-inferiority with the all oral 5FC + fluconazole regimen. For a low-dose 5-FC arm EFA of 0.35, non-inferiority compared to the concurrent controls will be established with a margin of 0.17. For an EFA better than $0.30 \log_{10}$ CFU/mL/day, survival is relatively similar across antifungal regimens, as per section 2.5 and Figure 2.5.

A subsequent statistical analysis of the ASTRO clinical trial has demonstrated that 30 to 40 patients with EFA is sufficient to determine a significant difference in EFA. This was based on a bootstrap analysis of the participants of the ASTRO trial that is documented in table 11.4.1 below.

Table 11.4.1: EFA Calculated with the ASTRO Study (n=378)

Replicate Size	500 Bootstrap EFAs from randomly selected replicates
N	Mean (95%CI)
10	-0.454 (-0.768, -0.219)
15	-0.450 (-0.688, -0.257)
20	-0.449 (-0.664, -0.269)
30	-0.445 (-0.608, -0.292)
40	-0.445 (-0.593, -0.308)
50	-0.446 (-0.569, -0.316)
378 Actual	-0.444 (-0.489, -0.399)

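### The synopsis trigger for the scheduled safety review does not count early deaths or culture-negative participants, so the review moves later as early mortality rises; Sections 4.1 and 10.3 give different triggers

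*Combined protocol and SAP*

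**What the plan says.** The review is described in three places.

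- Synopsis, Phase II Safety Analysis: the DMC conducts an "interim safety analysis after 10 participants are enrolled with >2 weeks of accrued data and calculable EFA".
- Section 4.1: "A DSMB review by the full committee will occur after 10 participants have been enrolled with >2 weeks of accrued data". There is no EFA condition.
- Section 10.3: "DSMB safety reviews will occur after 10 participants have been enrolled and have accrued approximately 2 weeks of follow-up data". There is no EFA condition, and the two weeks are approximate.

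I take the DMC of the synopsis and the DSMB of Sections 4.1 and 10.3 to be the same body and the review to be the same review, since the count and timing match. Section 2.6.1 has a related but separate rule: if EFA is consistently low "after 10 enrolled patients, then the trial will be suspended until an interim review" is done. That wording requires no accrued follow-up.

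Section 11.4.1 says what makes an EFA calculable: "non-sterile CSF culture at baseline and at least 1 follow up LP". Section 2.5 concedes: "Persons who rapidly die after diagnosis may not have a computed EFA". On culture, Section 5.1 says: "Approximately 10-15% of participants are estimated to be culture negative". On the timing of deaths, Section 2.2 says: "Approximately, half of the mortality occurs during the first two weeks and the other half during the next 18 weeks". None of the three trigger statements says how a participant who dies before two weeks is counted.

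**The concern.** A safety trigger should not depend on the outcome that it monitors. Under the synopsis wording it does, in two ways. A participant who dies before Day 14 cannot have more than two weeks of data, even if a Day 3 lumbar puncture made an EFA calculable. One who dies before any follow-up puncture has no EFA either. A culture-negative participant never has an EFA, alive or dead.

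The participants most informative about early harm therefore do not advance the count. If the lower dose raised early mortality, more people would be enrolled before the scheduled review came due. The three wordings also leave the sites and the board without a single rule to apply.

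**Working it through.** **Plan's own figure.** The count of 10 is stated without a derivation, so there is nothing to reproduce. The mortality input can be checked: Table 2.2 pools 18 deaths in 222 patients, and 18/222 = 8.1%.

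**Inputs**
- Culture-negative share c: 10% to 15% (Section 5.1).
- Two-week mortality m: 8.1% (Table 2.2, GCS=15 only). The trial also admits GCS below 15 by surrogate consent (Sections 5.3.3 and 5.3.4), so 8.1% may be low. The values 20% and 40% are assumptions used to show the range. Section 9.2.1 does give up to 20% for cryptococcal deaths, but not as a two-week figure.
- Accrual: up to 50 in up to 12 months, so 365.25/50 = 7.3 days per participant if even.

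**Formula.** A participant counts with probability q = (1 - m)(1 - c), taking death and culture result as independent. Expected enrolments until 10 count = 10/q. The 90th percentile comes from the negative binomial distribution. Delay = (10/q - 10) x 7.3 days.

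| m | 10/q at c=10% | 10/q at c=15% | Delay, days | 90th percentile |
|---|---|---|---|---|
| 8.1% | 10/(0.90 x 0.919) = 12.1 | 10/(0.85 x 0.919) = 12.8 | 15-20 | 14-15 |
| 20% (assumed) | 10/(0.90 x 0.80) = 13.9 | 10/(0.85 x 0.80) = 14.7 | 28-34 | 17-18 |
| 40% (assumed) | 10/(0.90 x 0.60) = 18.5 | 10/(0.85 x 0.60) = 19.6 | 62-70 | 24-25 |

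**How much is due to deaths.** With no deaths, culture-negatives alone give 10/0.90 = 11.1 to 10/0.85 = 11.8. At 8.1% mortality, deaths therefore add about 1.0 enrolment (12.1 - 11.1, or 12.8 - 11.8), which is about a week. At 40% they add 7.4 to 7.8. By the time 10 count, the expected number of early deaths is about 1.0 at m = 8.1% and 7.4 to 7.8 at m = 40% (18.5 x 0.40 and 19.6 x 0.40).

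**A scenario built from the plan's figures.** The synopsis links EFA below 0.20 with mortality above 50%, and Section 2.2 puts about half of deaths in the first two weeks. That is roughly 25% at two weeks for a failing regimen: 10/(0.90 x 0.75) = 14.8 to 10/(0.85 x 0.75) = 15.7 enrolled.

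**Dropping the EFA condition alone.** Set c = 0, as under Sections 4.1 and 10.3, and read the two-week condition as requiring survival. Expected enrolments are then 10/0.919 = 10.9, 10/0.80 = 12.5 and 10/0.60 = 16.7. The dependence on deaths remains.

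**With all of the first 10 counted to Day 14 or death.** The trigger stays at 10 enrolments for every m and c.

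**The case against.** The strongest reply is that only a meeting date slips. Section 10.3 says that data are unblinded, that investigators watch for unexpected concerns, and that any concern prompts an unscheduled DSMB evaluation. All available data are used at a review, and all deaths go to the IRB. The investigators, the DSMB chair and the sponsor can each suspend enrolment. In an open-label single-arm trial a run of early deaths would be seen. Sections 4.1 and 10.3 are also milder than the synopsis, and not counting deaths is one reading of the follow-up condition. At 8.1% mortality the effect of deaths is about one participant.

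Most of this stands. A reader might infer that early deaths would be hidden from the board. The documents do not support that: the trigger governs when the board meets, not whose data it sees. A reader might also infer that this is the only scheduled review and that later deaths and relapses go unexamined. No second date appears in the protocol, but Section 10.3 refers to a DSMB Charter that is not among the documents and speaks of reviews in the plural. Nor should participants who enrol while the report is prepared be charged to this defect, since they accrue under any trigger.

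The reply does not remove the need for a sound scheduled trigger. No mortality threshold is given for an unscheduled review. Section 9.4 says that death from the pre-existing meningitis is not an SAE. The one numeric early trigger, EFA below 0.2 in the synopsis, cannot use those who died without an EFA.

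**Conclusion.** The point holds. The synopsis makes the timing of the scheduled safety review depend on survival and culture status, and the three statements of the trigger disagree. The size is modest at the mortality the documents report: 12-13 enrolled instead of 10 at 8.1%, with deaths responsible for about one. It grows to 14-15 at an assumed 20% and 19-20 at an assumed 40%, so the delay is longest when the review matters most.

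These figures rest on even accrual, on independence of death and culture result, and on reading more than two weeks of data as requiring survival to that time. They ignore withdrawals and missed follow-up punctures. The plan's 36 out of 50 (72%) should not be multiplied by survival as well: the synopsis defines the 36 as participants with an EFA estimate, so some early deaths may already be allowed for.

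A large delay at expected mortality, or a failure to detect deaths at all, would be stronger claims than the documents support.

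**What to change.** State one trigger in the synopsis, Section 4.1, Section 10.3 and the DSMB Charter: the first 10 participants enrolled, whatever their survival, culture or EFA status, reviewed once each has reached Day 14 or died. Delete the calculable-EFA condition from the synopsis and report EFA at the review for those who have one.

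The cost is wording in three places and the Charter. The review will also have fewer than 10 EFA values. If every early death lacks an EFA, expect 10 x 0.90 x 0.919 = 8.3 down to 10 x 0.85 x 0.80 = 6.8. If early deaths have an EFA from a Day 3 puncture, expect up to 10 x 0.90 = 9.0. That is about 7-9 at 8-20% two-week mortality, and possibly fewer if mortality is higher. A second scheduled review is optional and not part of this point, because the Charter may already provide one.
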